8.2.5.2. Secondary Endpoints

Secondary endpoints are described in Section 3.2.

The analysis of the annualized rate of porphyria attacks requiring hospitalization, urgent healthcare visit, or IV hemin administration at home in all AHP patients (the FAS) over the 6-month double-blind period and the annualized rate of hemin doses will be conducted using the same approach as the primary analysis.

For the analysis of urinary ALA-related endpoints, the ALA levels will be compared between treatment arms using a mixed-effects model repeated measures (MMRM) with baseline ALA as a continuous covariate and fixed effect terms including treatment arms, stratification factors for AHP patients (prior hemin prophylaxis status and historical attack rates), visit and treatment by visit interaction. PBG-related endpoints will also be analyzed using this methodology.

Daily pain, nausea, and fatigue scores will be analyzed separately using the area under the curve (AUC) approach: the AUC over 6 months in the respective score will be calculated for each patient, and the mean AUC will be compared between treatment arms in an ANCOVA model. The change from baseline in PCS of SF-12 at 6 months will be analyzed use an MMRM model. Details will be described in the SAP.

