## 5.10. Analyses for the Entire Study

The study design includes a 6m-DB period and an OLE period. The primary objective is to evaluate the efficacy and safety of givosiran compared with placebo during the 6m-DB period. In addition, the long-term efficacy and safety of givosiran during the entire givosiran treatment period (beyond 6m-DB) will be characterized for the All Givosiran Treated Set. For patients who received placebo in the 6m-DB period and givosiran in the OLE period, the intra-patient comparison of the two treatment periods will be conducted to assess the trajectory changes for selected efficacy parameters.

The detailed definitions for different treatment periods are as the following.

- **6m-DB Period**

The treatment comparison of givosiran versus placebo will focus on the 6m-DB period, defined as below:

- 1) For patients who received at least one dose of givosiran during the OLE period, all assessments collected prior to the first dose of givosiran in the OLE period will be included in the 6m-DB period. All data will be included in the summary tables and figures.
- 2) For patients who discontinued treatment and did not receive any givosiran dose in the OLE period, all assessments will be included in the 6m-DB period. Assessments collected within given time windows (details listed in below table) will be included in summary tables/figures and those outside the time windows will be listed only unless specified otherwise (e.g., AEs in Section 6.8 ).

Endpoint	Windowing rule for patients who did not enter OLE
Safety and PD endpoints	Assessments with onset date within 28 days of the last dose [1]
Attacks and hemin use related endpoints	Data collected on or before the earlier of 1) Day 162 which is the start day of Month 6 visit window; and 2) end of study (EOS) date.

Endpoint	Windowing rule for patients who did not enter OLE
Other clinical efficacy endpoints	Assessments collected on or before Day 183.

[1] In a rare situation that a patient did not discontinue 6m-DB and did not enter OLE, all data will be included in summary. For AE summary, related AEs will be considered as TEAE and included in summary tables regardless of time window.

- **OLE Period**

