## 6.5. Efficacy Analysis

All efficacy endpoints will be analyzed in both AIP and AHP patients. Model-based analysis for AIP and AHP patients will adjust for the two stratification factors, i.e. use of hemin prophylaxis at screening (Y/N) and historical AAR prior to randomization (High/Low), unless otherwise specified. For analysis of AHP patients, AHP type (AIP versus non-AIP) will not be included in the model due to the small number of non-AIP patients.

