baseline in weekly mean scores. For each of the measures, the AUC of change from baseline will be compared between two treatment arms using ANCOVA model with fixed effects of treatment arms and two stratification factors. In addition, the average weekly score change from baseline over 6 months will also be calculated and analyzed using ANCOVA.

Symptoms are expected to be elevated during porphyria attacks. This AUC approach encapsulates the peaks of these symptoms during attacks as well as lingering chronicity of these symptoms throughout the entire treatment period. AUC approaches have been used in other episodic conditions to compare both the severity and duration of pain across groups.

The weekly mean score will be calculated using the following algorithm:

1. A completed week will be defined as a week where a patient completes 4 or more daily entries in a week, which is consistent with other diary-based PRO research. The available eDiary entries for a completed week will be averaged to determine the weekly symptom score.
2. A missing week will be defined as a week where a patient is missing 4 or more daily entries. In a missing week, if there is one or more recorded attack days during the week, the mean score will be derived based on the following rules:
  - If there are 1 or more completed attack day diary entries, the mean weekly score will be computed as an average of the daily entries for that week.
  - If there is no completed attack day diary entry, the weekly mean score will be imputed using the average of all non-missing attack-week weekly mean scores within the same treatment period for the patient. If there's no non-missing attack week score, the weekly mean score will be imputed by the worst weekly mean scores within the same treatment period for the patient.

Patients are expected to have elevated symptom scores during porphyria attacks, which can span over multiple days. This algorithm intends to preserve any completed eDiary entries collected during days associated with attacks.

3. In a missing week without any attack days, the weekly mean score will be imputed by the last observed non-missing week without any attack days. If there is no last observed non-missing week without any attack days, the imputation will be based on baseline observation carried forward (BOCF).

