The SF-12 scores are obtained using the Optum (PRO CoRE 1.3 Smart Measurement® System) software with the 2009 U.S. general population t-scores applied. For the Physical Component Summary (PCS) of SF-12 score, change from baseline at Month 6 in AIP patients (FASAIP) will be analyzed using an MMRM model with baseline score as a continuous covariate, fixed effect terms including treatment arms, stratification factors, visit (Month 3 or Month 6), and visit by treatment interaction.

All secondary endpoints defined for the AIP patients will also be analyzed for the AHP patients using similar methods.

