For the secondary endpoints daily worst score of pain, nausea, and fatigue, the AUC over 6 months will be derived by first calculating the weekly mean scores (Section 6.5.2).	Updated to address regulatory feedback on missing data handling and justification of AUC method.

## 7.2. Changes in SAP Amendment 2

In the SAP Amendment 2, detailed analyses for the entire study including OLE period are added. Amendment 2 will be signed off before the final analysis of the 6-month double-blind (6m-DB) data and the unblinding of treatment assignments.

In this version, a new analysis population All Givosiran Treated Set is added, additional subgroups of the All Givosiran Treated Set were defined to accommodate analysis of the different givosiran doses allowed in the OLE period with Protocol Amendment 3, and different treatment periods are defined to allow for the analysis of data in the overall study. In addition, Per Protocol Set is defined to allow for an evaluation of the primary endpoint in the subset of patients who fulfill the protocol in terms of the eligibility requirements, adherence to the study drug and outcome assessments. A few minor updates are made to the analysis of the 6m-DB period, e.g., zero-inflated negative binomial regression model is added to analyze components of attacks. For the analysis of worst scores of pain, fatigue, and nausea, the following updates are made:

- The AUC of weekly scores is updated as the AUC of change from baseline in weekly scores. Note that with an ANCOVA analysis adjusted for baseline, using the actual score or change from baseline as a response variable will yield the same estimate of treatment difference and p value. This update is made to allow for a direct estimate of the LS mean change from baseline in each treatment arm.
- The mean weekly score change from baseline over 6 months is defined for analysis, which is mathematically similar to the AUC of change from baseline in weekly score but is clinically meaningful and interpretable.
- The testing order of daily worst scores of fatigue and nausea are switched because the mean nausea scores at baseline are low therefore less likely to show improvement with treatment.

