**9.1.3. Analysis of ALA Endpoint**

**9.1.3.1. Primary Analysis Using ANCOVA/Multiple Imputation**

The primary analysis to evaluate the treatment effect in ALA at Month 3 is an ANCOVA model, with multiple imputation (MI) assuming missing at random (MAR) in case of missing data at Month 3. The ANCOVA model includes baseline ALA as a continuous covariate and fixed effect terms including treatment arm and stratification factors for AIP patients (prior hemin prophylaxis status and historical attack rates). The significance level for the comparison at the interim is 0.001 (2-sided). Any ALA values measured within 3 days after hemin use will be excluded from the ALA analysis and will be treated as missing. The Least Square (LS) means, SEMs and 95% confidence intervals (CIs) for the LS means, difference in LS Means, and corresponding 95% CIs and p-value will be presented.

Missing data at Month 3 will be multiply imputed separately for each treatment arm using the Markov Chain Monte Carlo (MCMC) method following the MAR assumption. Treatment arm, the stratification factors, ALA measurements at baseline, Week 2, Month 1 and Month 2 will be included in the imputation model. One hundred imputed datasets will be generated using the SAS PROC MI procedure. Each of the imputed datasets will then be analyzed via the primary ANCOVA model. The LS means and standard errors will be combined using SAS PROC MIANALYZE to produce inferences including treatment difference in LS means, 95% CI for the treatment difference, and the p-value. Point estimates (LS means and treatment difference) will be calculated as the average of the 100 complete-data estimates. A total variance estimate will be calculated as a weighted sum of within-imputation variance, which is the average of the complete-

data variance estimates, and a between-imputation variance term. The sample code for performing the primary analysis is provide in Section 9.1.

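### The ANCOVA for the pain, fatigue and nausea AUC lists no baseline covariate in SAP 6.5.2, although SAP 7.2 treats it as baseline-adjusted

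*SAP*

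**What the plan says.** SAP 6.5.2 forms weekly mean scores for pain, fatigue and nausea, subtracts the baseline score, and takes the AUC of these changes over 6 months. That AUC "will be compared between two treatment arms using ANCOVA model with fixed effects of treatment arms and two stratification factors". The companion analysis, of the average weekly change, is called ANCOVA with no terms given.

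SAP 7.2, in its list of updates to these three endpoints, makes this remark: "with an ANCOVA analysis adjusted for baseline, using the actual score or change from baseline as a response variable will yield the same estimate". The remark covers the p value as well. The reason it gives for moving from score to change is a separate one: "This update is made to allow for a direct estimate of the LS mean change from baseline in each treatment arm".

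Other models in the SAP name their baseline term. The SF-12 PCS model in 6.5.2 has "baseline score as a continuous covariate, fixed effect terms including treatment arms, stratification factors", among other terms. For the interim ALA analysis, SAP 9.1.3.1 states: "The ANCOVA model includes baseline ALA as a continuous covariate and fixed effect terms including treatment arm and stratification factors". The ALA and PBG model in 6.5.2 does likewise.

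The general rule in SAP 6.5 is that "Model-based analysis for AIP and AHP patients will adjust for the two stratification factors"; it mentions no baseline value. Protocol 8.2.5.2 says only that "the mean AUC will be compared between treatment arms in an ANCOVA model" and leaves the details to the SAP.

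**The concern.** A programmer working from 6.5.2 would fit treatment and two factors to a change score. A programmer working from 7.2 would add the baseline score. Both models can be run, and they give different estimates and p values.

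These endpoints are under type I error control. SAP 5.7 tests them in fixed sequence at 0.049, and in the order of SAP 3.2.2 a non-significant pain result stops fatigue, nausea and SF-12 PCS. The primary endpoint and the five secondary endpoints ahead of pain do not depend on this. What is at stake is precision on the late endpoints, and having one settled p value for each of them before unblinding.

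**Working it through.** **1. Does the equivalence in SAP 7.2 hold?** Let b be a patient's baseline score and T the duration. Then AUC of change = AUC of score − T·b. If T is common and b is in the model, subtracting T·b alters only the coefficient of b, so the treatment estimate, SE and p value are identical. If b is not in the model, the two treatment estimates differ by T times the adjusted baseline difference between arms.

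Check on one simulated data set (70 patients, 24 weeks, assumed correlation 0.6):

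| Model | AUC of score | AUC of change |
|---|---|---|
| With baseline | −22.93, SE 9.92, p 0.0239 | −22.93, SE 9.92, p 0.0239 |
| Terms as in 6.5.2 | −24.78, SE 11.88, p 0.0409 | −21.85, SE 10.59, p 0.0429 |

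The gap in the second row is −24.78 + 21.85 = −2.93, which is 24 weeks times a chance baseline difference of −0.122. So the 7.2 statement is true only if baseline is a covariate.

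**2. Cost in precision.** The documents give no correlation, SD or power for these scores, so the inputs are assumed: ρ is the baseline-to-follow-up correlation and k is follow-up SD divided by baseline SD. In units of the baseline variance:

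- unadjusted change: 1 + k² − 2ρk
- baseline-adjusted: k²(1 − ρ²)
- excess: (1 − ρk)², where ρk is the regression slope
- ratio R = 1 + (1 − ρk)² / [k²(1 − ρ²)]

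Example, ρ = 0.5 and k = 0.8: (1 + 0.64 − 0.80) / (0.64 × 0.75) = 0.84 / 0.48 = 1.75, and 70 / 1.75 = 40.

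Each cell gives R, then the large-sample power of the unadjusted test when the adjusted test has 80% at two-sided 0.049:

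| | ρ = 0.3 | ρ = 0.5 | ρ = 0.7 |
|---|---|---|---|
| k = 0.8 | 1.99; 51% | 1.75; 56% | 1.59; 60% |
| k = 1.0 | 1.54; 62% | 1.33; 68% | 1.18; 73% |
| k = 1.3 | 1.24; 71% | 1.10; 76% | 1.01; 80% |

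At ρ = 0.5, 70 patients act like 40 (k 0.8), about 52 (k 1.0) or about 64 (k 1.3).

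**3. How often the conclusion changes.** Simulation with 35 per arm, two binary factors, tests at 0.049 and 20,000 trials per row:

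| ρ, k | Power unadjusted / adjusted | Disagree |
|---|---|---|
| 0.7, 1.3 | 77.6% / 77.5% | 2.9% |
| 0.5, 1.3 | 73.7% / 76.9% | 8.1% |
| 0.5, 1.0 | 65.5% / 77.3% | 17.2% |
| 0.5, 0.8 | 54.4% / 77.4% | 28.2% |

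**4. Type I error.** Under the null (ρ 0.5, k 1.0) the levels are 4.86% unadjusted and 4.95% adjusted, with 4.71% discordant. The chance that at least one version falls below 0.049 is (4.86 + 4.95 + 4.71) / 2 = 7.3%. This matters only if the model were chosen after unblinding.

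**5. A smaller gap: AUC duration.** The equivalence also needs a common T. Under SAP 5.10, for patients who enter the extension, "all assessments collected prior to the first dose of givosiran in the OLE period will be included in the 6m-DB period", so T varies, and no time-standardisation of the AUC is stated. With baseline in both models (4,000 trials), the score and change estimates differ by 0.05 SE on average (largest 0.20) for durations of 162–176 days, by 0.07 SE (largest 0.39) for 162–183 days, and by zero for a common duration.

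**The case against.** The strongest reply is that 6.5.2 is merely incomplete. It uses the word ANCOVA and lists only fixed effects, and elsewhere the SAP names the continuous covariate apart from the fixed effects. The 7.2 note points towards adjustment, and nothing says the model is unadjusted. This stands as a reading of intent, and omission is the likeliest explanation. It does not complete the specification: the response is already a change score, so the listed model runs as written, and a general mathematical remark in 7.2 is not a model statement.

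A second reply is that 7.2 is a change history. The sentence, however, supports the current Amendment 2 analysis and is not superseded wording. It is also fair that the equivalence is a supporting note and not the stated reason for the change.

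Third, the size is assumed throughout and includes almost no loss. Disagreement also falls as power rises: at about 95% adjusted power it is roughly 9% (ρ 0.5, k 1.0), 18% (ρ 0.5, k 0.8) and 1% (ρ 0.7, k 1.3). This stands, and the range should be read accordingly.

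Fourth, the duration effect is immaterial, and the average weekly change is in effect a time-standardised AUC. This largely stands, and the point is kept as secondary.

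Finally, the protocol on file dates from March 2021, and its Amendment 5 summary describes double-blind results. A wording change made now may therefore come after unblinding. The SAP itself places its sign-off before unblinding, which is where the correction belongs.

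**Conclusion.** The inconsistency is real and should be fixed. SAP 6.5.2 as written gives an unadjusted comparison of change scores, SAP 7.2 presupposes adjustment for baseline, and no other text supplies the term. The literal model is valid under randomisation, so the issue is precision and an unambiguous specification, not bias. The variance penalty ranges from 1% to 99% over the assumed ρ of 0.3–0.7 and k of 0.8–1.3; it is 33% at ρ 0.5 with equal SDs. It is confined to pain, fatigue and nausea and, through the fixed sequence, to whether SF-12 PCS is reached. That the sections disagree, and that the equivalence fails without baseline, does not rest on any of these assumptions.

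**What to change.** In SAP 6.5.2, add the baseline score of the respective symptom, as defined in SAP 5.4, as a continuous covariate. Do so for both the AUC of change and the average weekly change, in FAS_AIP and FAS. If the 7.2 equivalence is to stand as worded for the AUC, also compute the AUC over a common duration or divide it by each patient's duration. If an unadjusted model is in fact intended, say so in 6.5.2 and delete the equivalence note from 7.2.

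The cost is one or two sentences. The baseline score is already collected and derived, and no new data or patients are needed. The change belongs before unblinding. If that point has passed, the sponsor should document which model was prespecified and report both.

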### **6.5.3. Exploratory Endpoints**

The continuous exploratory endpoints in AIP patients for the 6m-DB period including EQ-5D-5L index score will be analyzed using an MMRM model similar to the one employed for the secondary endpoint PCS SF-12.

Patient Global Impression of Change (PGIC) at Month 6 and Month 12 will be summarized descriptively with number and proportion of patients in each category, as well as the two combined categories of “Improved” and “No Change or Worsening”. The category of “Improved” includes minimally improved, much improved, and very much improved. The category of no change or worsening includes no change, very much worse, much worse, and minimally worse. Mantel Haenszel chi-square test will be used to compare the proportion of “Improved” between the two treatment arms. Odds ratio will be estimated.

Missed days of work/school in the past 4 weeks at Month 6 will be summarized descriptively.

Porphyria Patient Experience Questionnaire (PPEQ) will be summarized descriptively.

For endpoints assessed in patients with any AHP (FAS) over the 6m-DB period, the analyses will be conducted using methods similar as those employed for the AIP patients (FASAIP).

For EQ-5D-5L, a categorical summary of the numbers and percentages of patients reporting each ordinal response within each EQ-5D domain will also be presented.

Analgesic medication use during the 6-month DB period will be summarized as follows:

- Number (%) of patients who took at least one analgesic medication by category (opioid, non-opioid, either opioid or non-opioid) and PT during periods of screening, Month 1 to 3, Month 4 to the end of 6m-DB period, and during the 6m-DB period.
- Descriptive summary on proportion of days with analgesic use during the 6m-DB period by category (opioid, non-opioid, either opioid or non-opioid).

Refer to Appendix 9.5 for the detailed rules in categorizing analgesic medication and opioid/non-opioid.

Data collected during the OLE period will be summarized descriptively. For daily worst pain/nausea/ fatigue scores collected during the OLE period, change from baseline in weekly mean scores will be summarized descriptively.

#### **6.5.4. Subgroup Analysis**

For the primary endpoint, subgroup analyses will be conducted to assess the consistency of treatment effect for the AIP and AHP patients during the 6m-DB period. A negative binomial regression model will be fit to estimate the treatment effect within each subgroup. The model includes treatment arms as a fixed effect and each patient’s time on study as an offset variable. An estimated ratio of mean AARs between the two treatment arms with the corresponding 95% CI will be estimated for each subgroup. If the number of patients in either treatment arm of a subgroup is less than 10, only descriptive statistics will be presented.

- Age at Screening (< or ≥ median age in the overall population)
- Race (White or Non-white)
- Sex (Female or Male)
- Region group 1: North America (including US and Canada) or Other (outside North America)
- Region group 2: Europe or Other (outside Europe)

- Baseline BMI (<25 or ≥25)
- Prior hemin prophylaxis status (Yes or No)
- Historical attack rates prior to randomization based on the hemin prophylaxis status prior to the study (high or low)
- For patients on a hemin prophylaxis regimen at the time of screening, if  $AAR \geq 7$ , the patient is considered having high attack rates prior to the study. For patients who were not on a hemin prophylaxis regimen at screening,  $AAR \geq 12$  is considered with high attack rates.
- Prior chronic opioid use when not having attacks (Yes or No)
- Prior chronic symptoms when not having attacks (Yes or No)

Other subgroups may be examined, if deemed appropriate.

The subgroup analyses may also be performed for other secondary endpoints.

The number of non-AIP patients is anticipated to be only a few. Descriptive statistics on the primary and secondary endpoints will be provided by treatment arm for non-AIP patients.

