1. INTRODUCTION

1.1. Disease Overview

The acute hepatic porphyrias (AHPs) are a family of rare, serious and life-threatening metabolic disorders predominantly caused by a genetic mutation in 1 of the 8 enzymes responsible for heme synthesis (Figure 1). The AHPs include Acute Intermittent Porphyria (AIP), Hereditary Coproporphyrin (HCP), Variegate Porphyria (VP), or ALA dehydratase deficient porphyria (ADP) (1); AIP is the most common AHP type. All AHP are due to autosomal dominant loss-of-function mutations in enzymes in the heme biosynthetic pathway, with the exception of ADP, which is the result of autosomal recessive mutations (2, 3).

Figure 1: Heme Biosynthetic Pathway and Enzyme Deficiency Resulting in Acute Hepatic Porphyria

Reference: James, et al 2000 (4)

Acute attacks are triggered by stress factors that induce the expression of aminolevulinic acid synthase 1 (ALAS1), which is the rate limiting step in heme synthesis. In women, attacks often occur around the menstrual cycle due to changes in ALAS1 expression from hormonal fluctuations. The induction of ALAS1, upstream of heme synthesis enzyme deficiencies, results in increased flux through the heme synthesis pathway and marked accumulation of the neurotoxic

porphyrin precursors, aminolevulinic acid (ALA) and/or porphobilinogen (PBG), the causal factors driving clinical manifestations of disease.

Disease symptom onset in AHP patients typically occurs after puberty, with women (~80%) more commonly affected than men (5). Patients experiencing acute attacks present with highly morbid and potentially life-threatening symptoms that relate to widespread dysfunction across the central, peripheral, and autonomic nervous system. The most debilitating and frequent symptom during acute attacks is diffuse, severe neurovisceral pain, most often in the abdomen, back, or limbs. Other common attack signs and symptoms include nausea and vomiting, fatigue, hypertension, tachycardia, motor weakness, hyponatremia, and mental status changes (3, 6). The attack manifestations and pain are often so severe that they require hospitalization, supportive care and the use of high-dose intravenous opioids (7). Limb numbness, weakness or paresis due to a sensory or motor neuropathy, respectively, can also occur, with progression to paralysis, respiratory failure and death (1, 8, 9).

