## 5. GENERAL STATISTICAL METHODS

### 5.1. Determination of Sample Size

The planned total enrollment for the study is approximately 74 patients, including approximately 70 AIP patients.

Seventy patients will yield at least 90% power to detect a 45% reduction in the annualized attack rate at a 2-sided 5% significance level assuming a mean annualized attack rate of 8, a standard deviation (SD) of 5 in the placebo arm (mean/SD of 4/2.9 for 6 months to preserve the over-dispersion of 3.8), and a mean annualized attack rate of 4.4 with SD of 3 in the givosiran arm (mean/SD of 2.2/1.8 for 6 months to preserve the over-dispersion of 4.2), using a negative binomial model. This study design will still have at least 80% power even if the dropout rate is as high as 15% under the same assumptions.

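### SAP 6.5.4 sets out to assess consistency of the primary effect across subgroups but never estimates the between-level contrast that measures it

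*SAP*

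**What the plan says.** SAP 6.5.4 states its aim for the primary endpoint as follows: "subgroup analyses will be conducted to assess the consistency of treatment effect for the AIP and AHP patients during the 6m-DB period". It lists ten two-level factors: age, race, sex, two regional splits, BMI, prior hemin prophylaxis, historical attack rate, chronic opioid use and chronic symptoms.

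The method is one model per level: "A negative binomial regression model will be fit to estimate the treatment effect within each subgroup". On its terms the SAP says "The model includes treatment arms as a fixed effect", plus time on study as an offset. The output is likewise per level: "An estimated ratio of mean AARs between the two treatment arms with the corresponding 95% CI will be estimated for each subgroup". Small levels are not modelled: "If the number of patients in either treatment arm of a subgroup is less than 10, only descriptive statistics will be presented".

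The SAP contains no treatment-by-subgroup term, ratio of rate ratios or heterogeneity measure. Its only interactions are visit by treatment, in the repeated-measures models. Protocol 8.2.2 leaves subgroup methodology to the SAP. Neither document says what a consistent or an inconsistent display would look like.

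**The concern.** Consistency is a statement about the difference between the effects in two levels. The plan reports each effect but not the difference, and gives no guidance on comparing them. A reader left with two intervals may check whether each excludes 1. With levels of about half the trial or less, that check depends largely on each level's power. A uniform effect can then look as if it works in one group only, and a real loss of effect can be put down to small numbers. Either way, the primary conclusion could be wrongly restricted or wrongly extended to a group of patients.

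**Working it through.** **Inputs (SAP 5.1).** 70 patients, 1:1. Six-month means are 4 (placebo) and 2.2 (givosiran), a ratio of 0.55. The dispersions k follow from the annual mean and SD:
- placebo: (25 − 8)/64 = 0.266, i.e. 1/k = 3.8, as stated
- givosiran: (9 − 4.4)/4.4² = 0.238, i.e. 1/k = 4.2, as stated

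**Formula.** For n patients per arm, the variance of the log rate ratio is [(1/4 + 0.266) + (1/2.2 + 0.238)]/n = 1.208/n. Also |log 0.55| = 0.598. Power is Φ(0.598/SE − 1.96); the other tail is negligible.

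**The plan's own figure first.** The SAP states "Seventy patients will yield at least 90% power to detect a 45% reduction in the annualized attack rate at a 2-sided 5% significance level". At n = 35, SE = 0.186 and z = 3.22, so power is 89.6%; simulating the fitted model (2,000 runs) gave 90.6%. With 15% dropout (n = 29.75), power is 84.3%, against the stated minimum of 80%. The design figures are reproduced.

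**Power within a level.**
- 50:50 (n = 17.5): SE 0.263, z 2.28, power 62%. Using 168 days instead of six months gives about 60%.
- 60:40 (n = 21 and 14): 70% and 53%
- 70:30 (n = 24.5 and 10.5): 77% and 42%

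**Chance of a mixed display.** I call a factor mixed when exactly one of its two CIs excludes 1. This definition is mine, not the SAP's. With level powers pA and pB:
- uniform effect: pA(1 − pB) + pB(1 − pA)
- effect absent in one level, power p in the other: 0.95p + 0.05(1 − p)

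At 50:50 these are 2 × 0.624 × 0.376 = 47% and 0.95 × 0.624 + 0.05 × 0.376 = 61%.

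| Split | Uniform | Absent in smaller level | Absent in larger level |
|---|---|---|---|
| 50:50 | 47% | 61% | 61% |
| 60:40 | 49% | 68% | 53% |
| 70:30 | 54% | 74% | 43% |

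Simulation with maximum-likelihood fits (1,500 runs per cell) agreed: 46% against 62–63% near 50:50, and 54% against 73.5% or 45% at 25/10 per arm.

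**Sensitivity at 50:50 (uniform, then absent in one level).**
- ratio 0.60, N = 70: 50%, 51%
- ratio 0.55, N = 90: 39%, 71%
- ratio 0.37, N = 70: 12%, 89%
- ratio 0.25, N = 70: 1.5%, 94%

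The last two ratios match the 63–75% reductions from run-in that Protocol 1.5 reports for Phase 1. N = 90 is the upper size once considered for the sample size reassessment (SAP 7.1).

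**The missing contrast.** The two levels contain different patients, so the variances of their log ratios add. In a level with no effect, both arms have mean 4. Keeping each arm's own k, that level's variance is [(1/4 + 0.266) + (1/4 + 0.238)]/n = 1.003/n.
- 50:50: SE = √(1.208/17.5 + 1.003/17.5) = 0.355; 0.598/0.355 = 1.68; power 39%
- 70:30, absent in smaller level: SE 0.381, power 35%
- 70:30, absent in larger level: SE 0.395, power 33%

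Simulated power was 33–42%, and the false-positive rate under a uniform effect was 4.7–5.7%. The 95% CI is the estimate multiplied and divided by about 2.0 to 2.2.

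**The case against.** **No reading rule is prescribed.** The SAP plans estimates with intervals. It gives no subgroup p-values and does not say that a CI including 1 signals inconsistency. Judged instead by whether the two point estimates fall on opposite sides of 1, the display separates well: 2% under a uniform effect against 50% when it is absent in one level (50:50). This stands. The mixed rates describe one tempting way to read the table, not a rule in the plan.

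**The contrast can be derived.** A reader can compute the ratio of ratios and its CI from the two planned estimates, because the levels are independent. This also stands. It would be wrong to infer that the planned output cannot address consistency; what is missing is the derived quantity and a statement of how to judge consistency.

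**Does the display look the same whether or not the effect is uniform?** A reader might infer so from the 70:30 row, where 54% compares with 43%. The design figures do not support that in general: the gap is 47% to 61% at an even split, and 54% to 74% when the effect is missing in the smaller level. Near-equality needs an uneven split with the null in the larger level, or an effect weaker than planned. SAP 7.1 reports more patients randomized than expected, and Phase 1 reductions were larger than 45%; both would widen the gap.

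**Does the 10-per-arm rule need to go?** The Protocol describes symptomatic patients "with women (~80%) more commonly affected than men". At 20% of 70, men would number about 14, or 7 per arm, and would get descriptive statistics only. But that figure describes the disease, not this trial's enrolment, and avoiding model fits on so few patients is defensible. A modelled ratio for such a level would lean on an assumed common dispersion. The rule can stay.

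**Conclusion.** The gap is real: SAP 6.5.4 names consistency as its purpose and omits the quantity that measures it, and no other part of the documents supplies it. That holds whatever the effect size.

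The practical size is moderate. At the design values a uniform effect gives a mixed pair of CIs for about half of modelled factors (47–54%), against 43–74% when the effect is absent in one level. These figures assume splits from 50:50 to 70:30, equal arms within levels, the same placebo rate and dispersion in each level, and my definition of mixed. They should not be turned into a count over all ten factors, because factors overlap and some levels may fall under the 10-per-arm rule.

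Severity is minor. The subgroup analyses lie outside the fixed testing sequence in SAP 5.7, and no decision depends on them. The change is a cheap improvement.

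**What to change.** In SAP 6.5.4, for each factor where both levels are modelled, add the ratio of the two rate ratios with its 95% CI. Take it from a treatment-by-subgroup term in one negative binomial model, or directly from the two level estimates by adding the variances of the log ratios. Label it as the exploratory measure of consistency, and state that consistency is not to be judged by whether individual subgroup CIs exclude 1.

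Add a table note that the contrast has only about 35–40% power (33% in the least favourable split calculated) to detect complete loss of effect in one level, so a wide interval containing 1 is not evidence of consistency.

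The cost is a few lines of SAP text and one extra column computed from data already in the analysis file. The primary test, the significance level and the 10-per-arm rule are unchanged.
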